10.3. Physical Examinations

A complete PE will be done in the screening period where at a minimum, assessments of the cardiovascular, respiratory, gastrointestinal and neurological systems; breast and genitourinary exams are excluded. Any abnormality identified at the screening PE will be recorded as medical history.

10.4. Clinical Laboratory Assessment

Clinical laboratory assessments are listed in Table 3 below. Certain clinical laboratory assessments (eg, comprehensive metabolic panel, hematology, urinalysis and serum pregnancy testing) will be performed for screening purposes only, whereas other clinical laboratory assessments (eg, urine drug, and alcohol screening) will be performed at various study time points.

Hematology, serum chemistry and urinalysis at screening will be summarized and listed. In data listings, any out of reference range values will be flagged as high/low, further clinically significant lab results will be flagged in listings if applicable.

Abnormal laboratory assessments deemed clinically significant by the investigator will be reported as an adverse event.

All other laboratory results, including pregnancy test, drug screen, and alcohol screen, will also be presented in data listings.

Table 3 List of Laboratory Tests

Hematology: - Complete blood count (CBC), including platelet count and white blood cell count (WBC) with differential - Complete blood count (CBC), - Albumin (ALB) - Alkaline phosphatase (ALK-P) - Alanine aminotransferase (ALT; SGPT)

TT · I ·	A C CACE
Urinalysis:	- Aspartate aminotransferase (AST;
- Appearance - Bilirubin - Color - Glucose - Ketones - Nitrite - Occult blood - pH - Protein - Specific gravity - Urobilinogen	SGOT) - Blood urea nitrogen (BUN) - Calcium (Ca) - Chloride (Cl) - Creatinine - Creatine kinase - Gamma-glutamyl transferase (GGT) - Globulin - Glucose - Lactate dehydrogenase (LDH) - Phosphorus - Potassium (K)
*Serum Pregnancy Screen	 Sodium (Na) Magnesium Total bilirubin Direct bilirubin
Drug Screen (urine)	Total cholesterolTotal proteinTriglycerides
Alcohol Screen	- Uric acid
	- Thyroid stimulating hormone
	(TSH)(screening only)

^{*}Pregnancy screening is required for all females of childbearing potential. Female subjects who have undergone surgical sterilization, who are post-menopausal (defined as >1 year of amenorrhea), who have medically documented ovarian failure (defined as serum estradiol and follicle-stimulating hormone [FSH] levels within the institutional postmenopausal range and a negative serum or urine β HCG) do not need to undergo pregnancy screening.

10.5. Pregnancy Testing

Pregnancy testing is required for all females of childbearing potential in the screening period unless otherwise exempt (see Table 3). Additional pregnancy tests may be performed, as deemed necessary by the investigator or required by local regulation, to establish the absence of pregnancy at any time during the study. A listing of pregnancy results will be presented.

10.6. Vital Signs

The following vital signs measurements will be reported for this study.

- Sitting systolic blood pressure (SBP), (millimeter of mercury [mmHg])
- Sitting diastolic blood pressure (DBP) (mmHg)
- Sitting heart rate (beats per minute [bpm])
- Sitting respiratory rate (breaths/minute)

• Body Temperature (°C)

These vital signs will be measured during the screening visit and each in-clinic scheduled visit, according to the schedule of activities.

The observed and change from baseline vital signs across all study periods will be summarized by visit. Change from XYWAV Conversion Day will also be summarized for visits after conversion. In addition, number and percentages of subjects with at least one abnormal vital signs (based on criteria at Table 4 below) will be summarized by visit.

A listing of vital signs with flagged abnormal values will also be presented.

Table 4 Vital Signs Predefined Markedly Abnormal Criteria

Parameter (unit)	Low	High
SBP (mmHg)	< 90 mmHg	> 140 mmHg; > 160 mmHg
DBP (mmHg)	< 50 mmHg	> 90 mmHg; > 100 mmHg
Heart rate (bpm)	< 60 bpm	> 100 bpm
Respiratory Rate	< 12 breaths/min	> 20 breaths/min
Temperature (°C)	< 36.0 °C	> 38.0 °C

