8.3.2. Vital Signs

- Vital signs to be measured (before blood collection, when applicable) will include oral temperature, heart rate (HR), respiratory rate (RR), and BP at the times specified in the SoA (Section 1.3).
- Blood pressure and pulse measurements will be assessed with a completely automated device.
- Blood pressure and pulse measurements should be preceded by at least 5 minutes of rest for the participant in a quiet setting without distractions (eg, television, cell phones).
- Vital signs will be measured in a semi-supine position after 5 minutes of rest period

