7.2. Baseline and Study Day Definitions

7.2.1. Baseline

For all safety assessments and effectiveness summaries across the study, study baseline will be defined as the last non-missing measurement collected/ assessed during the Baseline (Xyrem) Period in which participants remain on a stable Xyrem dose and regimen, with or without concomitant anticataplectics or stimulants. First dose of XYWAV will be administered in the first night of Visit 3. Assessment and data collected in the baseline period up till that night, will be included in this period.

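### SAP 10.6 calls vital signs sitting where the protocol specifies semi-supine, and its abnormality count does not separate findings new on XYWAV from those already present on Xyrem

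*SAP*

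**What the plan says.** **Position.** Protocol 8.3.2 states: "Vital signs will be measured in a semi-supine position after 5 minutes of rest period". SAP 10.6 lists "Sitting systolic blood pressure (SBP" and gives diastolic pressure, heart rate and respiratory rate the same sitting label; temperature carries none. SAP 7.6, which lists the departures from the protocol, mentions added and changed analysis sets and the severity grading of adverse events, but not the measurement position.

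**Abnormal values.** SAP 10.6 plans that the "number and percentages of subjects with at least one abnormal vital signs (based on criteria at Table 4 below) will be summarized by visit". Table 4 gives a low and a high limit for five parameters, with two high limits each for SBP (>140 and >160 mmHg) and DBP (>90 and >100 mmHg). Nothing conditions the count on the participant's value before the switch.

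**Other vital-sign outputs.** The same section plans three more:
- By-visit summaries: "The observed and change from baseline vital signs across all study periods will be summarized by visit".
- For post-switch visits, a further summary of the shift since the day of conversion.
- Participant-level data: "A listing of vital signs with flagged abnormal values will also be presented".

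Under SAP 7.2.1, "study baseline will be defined as the last non-missing measurement collected/ assessed during the Baseline (Xyrem) Period", and the first XYWAV dose is taken on the night of Visit 3.

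**The concern.** If sites follow the protocol, four of the five parameters will be reported with the wrong position in every vital-sign output. A reader could not tell whether the label or the conduct had changed.

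The abnormality count raises a separate issue. In a switch study, a reader of such a table wants to know who crossed a limit after moving to XYWAV and who came back within limits. A participant hypertensive on Xyrem and unchanged on XYWAV enters the count in the same way as a new case. For adverse events the SAP applies a rule of this kind: a treatment-emergent event must begin or worsen after the first XYWAV dose (SAP 10.2). Vital signs have no counterpart.

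The stakes are moderate. The protocol introduction argues for XYWAV partly on sodium load and blood pressure, and protocol 2.3.2 lists lower sodium-related risk as a possible benefit. Laboratory panels and ECG are for screening only (protocol 8.3.3 and 8.3.4). Apart from drug and alcohol screens, vital signs are therefore the only scheduled objective safety measure on XYWAV.

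**Working it through.** The documents give no vital-sign rates and no calculated figure on this point, so there is nothing to reproduce. The check is textual, with an illustration on assumed counts.

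**Step 1: position.** Protocol 8.3.2 says semi-supine; SAP 10.6 says sitting for four parameters; SAP 7.6 is silent. Both labels cannot describe the same measurement. Change within a participant does not depend on the label, provided every visit used the same position.

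**Step 2: what the by-visit count determines.** Take *N* participants measured at a Xyrem visit and at a XYWAV visit. Let *a* be the number abnormal on Xyrem, *b* the number abnormal on XYWAV, *n* the number newly abnormal and *r* the number resolved. Then

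- b = a + n − r, so the table yields n − r = b − a;
- n lies between max(0, b − a) and min(b, N − a);
- r = n − (b − a).

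With N = 100 (the planned enrolment, here assumed all measured at both visits) and assumed values of *a* and *b*:

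| a (Xyrem) | b (XYWAV) | Net change shown | Newly abnormal, possible range | Resolved, possible range |
|---|---|---|---|---|
| 10 | 10 | 0 | 0 to 10 | 0 to 10 |
| 30 | 30 | 0 | 0 to 30 | 0 to 30 |
| 30 | 40 | +10 | 10 to 40 | 0 to 30 |
| 40 | 30 | −10 | 0 to 30 | 10 to 40 |

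The net change is known exactly. The numbers newly abnormal and resolved are only bounded, and the bounds are wide.

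**Step 3: what counts as abnormal.** Read literally, one abnormal value in any parameter, in either direction, puts a participant in the count. If each of the five parameters had the same abnormality rate p, independently, the share with any abnormality would be 1 − (1 − p)^5. For assumed p of 2%, 5%, 10% and 15% this gives 9.6%, 22.6%, 41.0% and 55.6%. Pooling also dilutes a change in one parameter. With p = 5% throughout, halving one parameter's rate gives 1 − 0.975 × 0.95^4 = 20.6%, a fall of 2.0 points from 22.6%. Under this reading the higher cut-offs do no work, since an SBP above 160 is already above 140.

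**Step 4: whether other outputs supply *n* and *r*.**
- The change summaries describe the distribution of change (SAP 7.1: mean, SD or SE, median, minimum, maximum). They do not count crossings of a limit.
- Baseline is the last Xyrem value. If vital signs are taken at Visit 3 before that night's dose, change from baseline and change from conversion day coincide for later visits, so the second adds little.
- The flagged listing contains the information, but the reader must count by hand.

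**The case against.** The strongest reply is that the section already plans for change. The count is by visit and the switch falls on the night of Visit 3, so Xyrem and XYWAV visits stand side by side. Changes in SBP and DBP are summarised in their own right. The listing shows who was abnormal and when. Clinically significant worsening of vital signs is an adverse event under protocol Appendix 7 and, if it begins or worsens after the first XYWAV dose, appears in the treatment-emergent tables. Vital signs are not among the key endpoints, the study rationale in protocol 2.1 does not name blood pressure, and all analyses are descriptive.

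Most of this stands, and it rules out some stronger readings:
- A reader might infer that the table cannot show any change after the switch. The documents do not support that, because net change in prevalence is readable.
- A reader might infer that a fall in blood pressure would be hidden by slow heart rates. That could happen only within a pooled count; the SBP and DBP change summaries would still show the fall.
- A reader might take pooling as settled. It is one reading of ambiguous text. The layout of Table 4 and its second high cut-offs make a by-parameter table at least as plausible.
- A reader might infer that the position mismatch invalidates before-and-after comparison. It does not if the position was constant.

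The reply leaves two things unanswered: the contradictory label, and the absence of any table that counts limits crossed after the switch. The adverse-event route captures only what an investigator judges clinically significant.

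**Conclusion.** The point holds in a limited form. The position label contradicts the protocol and must be reconciled; the documents do not show which position sites used. The abnormality count gives net prevalence by visit, but not the numbers newly abnormal or resolved after the switch, and it leaves open how parameters, directions and the double cut-offs are combined.

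No size can be calculated from the documents. The ranges in the table rest on assumed counts with complete data at both visits, and the pooled percentages rest on assumed equal rates and independence. They show what the table leaves undetermined and do not predict results. Sample size, power and error rates are untouched. This is an inexpensive improvement to a safety table plus a wording correction.

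**What to change.** 1. Change the label in SAP 10.6 to match protocol 8.3.2. If sites measured sitting, record that in SAP 7.6 as a change, with the reason. Either way, outputs should state the position actually used.
2. Tabulate Table 4 by parameter, direction and cut-off, so that SBP above 140 and above 160, and DBP above 90 and above 100, each have their own row.
3. For visits after the first XYWAV dose and up to end of treatment or early discontinuation, add for each row: (a) participants abnormal now but not at the last Xyrem value, with those not abnormal on Xyrem as denominator; and (b) participants abnormal at the last Xyrem value and no longer abnormal, with those abnormal on Xyrem as denominator.
4. State that a Visit 3 reading taken before that night's dose counts as a Xyrem value, since the visit table in SAP 7.2.3 places Visit 3 in the intervention period.

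The data are already collected. The cost is a few lines of SAP text and one somewhat larger descriptive table.

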10.7. Electrocardiograms

Electrocardiograms will be reported during the Screening visit with the following ECG parameters:

- Overall ECG assessment:
 - o Normal
 - o Abnormal, not clinically significant
 - o Abnormal, clinically significant

A table of summary statistics will contain count and frequency for the discrete variables (normal, abnormal/not clinical significant, abnormal/clinical significant) and count. An ECG listing will also be presented.

10.8. Nausea Visual Analog Scale

Tolerability associated with Xyrem and XYWAV will be measured based on an NVAS assessment.

For NVAS, the baseline value is defined as NVAS evaluation performed daily over the last 7 days of the Xyrem-stable Baseline Period. For missing NVAS assessment handling, please see Section 7.2.4. The NVAS results for the baseline, end of treatment, and the change from the baseline period will be summarized with number and frequency of having nausea or not, and the mean (SD), median, and range. 95% CI of the mean change in NVAS from the baseline will be estimated. A listing will also be presented.

10.9. Suicidal Ideation and Behavior Risk Monitoring

XYWAV and Xyrem are considered CNS depressants. Columbia-Suicidal Severity Rating Scale (C-SSRS) will be administered to participants during the screening period to exclude any individuals with active suicidal ideation or behavior. A listing of C-SSRS scores will be presented.

10.10. Participant Health Questionnaire-9

The Participant Health Questionnaire-9 (PHQ-9) scale is a depression assessment that scores each of the 9 DSM-IV criteria for major depressive disorder with 4 scores (0 = not at all, 1 = several days, 2 = more than half of the days, 3 = nearly every day). Total scores are summed up to 27 across all 9 criteria with higher score suggesting a more depressed condition. For score interpretation, total PHQ-9 scores can be divided into 5 depression severity grades: 1-4 (minimal depression), 5-9 (mild depression), 10-14 (moderate depression), 15-19 (moderately severe depression) and 20-27 (severe depression).

A table with summary statistics for total scores and overall score interpretation categories will be presented. A listing will also be presented.

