13. Have a history or presence of any unstable or clinically significant medical condition, behavioral or psychiatric disorder (including active suicidal ideation), or history or presence of another neurological disorder or surgical history that might affect the participant's safety and/or interfere with the conduct of the study, in the opinion of the investigator
14. Display relevant suicidality as indicated by Columbia Suicide Severity Rating Scale (C-SSRS) ([Posner 2011](#)) evaluation at screening
15. Display moderate to severe depression as indicated by the Participant Health Questionnaire – 9 (PHQ-9) ([Kroenke 2001; Kroenke 2010](#)) at screening
16. Are a female participant who is pregnant or breastfeeding

Prior/Concomitant Therapy

17. Have undergone treatment with any prohibited central nervous system (CNS) agents, including but not limited to benzodiazepines, non-benzodiazepine anxiolytics/ hypnotics/ sedatives, neuroleptics, opioids, barbiturates, phenytoin, ethosuximide, or MCT inhibitors, eg, diclofenac, valproate, ibuprofen, within 2 weeks prior to enrollment. Discontinuation for the purpose of study enrollment is permitted only if considered safe by the investigator and approved by the Medical Monitors.

Prior/Concurrent Clinical Study Experience

18. Received any other investigational drug within 30 days or five half-lives (whichever is longer) prior to screening, or plan to use an investigational drug (other than the study intervention) during the study.

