8.3.8. Participant Health Questionnaire-9 (PHQ-9)

The PHQ-9 represents a depression assessment scale that scores each of the nine DSM-IV diagnostic criteria for major depressive disorder in accordance with guidelines presented in the Diagnostic and Statistical Manual Fourth Edition (DSM-IV). The PHQ assessment can be administered by self, study staff in person, or by telephone and is used to facilitate diagnosis of major depression and assessment of symptom severity. It is validated and documented in a variety of populations and is available in a variety of languages ([Kroenke 2001](#)).

In this study, PHQ-9 will be self-administered during the screening visit, as indicated in the SoA ([Section 1.3](#)). Participants will be evaluated and an assessment of risk will be made by a qualified mental health professional, if major depression is suspected or active suicidal ideation is identified.

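### The PHQ-9 severity grades in SAP 10.10 begin at 1, so a total score of 0 falls in none of the category rows of the planned table

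*SAP*

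**What the plan says.** SAP 10.10 describes the PHQ-9 as a scale that "scores each of the 9 DSM-IV criteria for major depressive disorder with 4 scores (0 = not at all, 1 = several days", with 3 as the highest item score. It adds: "Total scores are summed up to 27 across all 9 criteria". For interpretation it states that "total PHQ-9 scores can be divided into 5 depression severity grades: 1-4 (minimal depression"), followed by "5-9 (mild depression), 10-14 (moderate depression), 15-19 (moderately severe depression) and 20-27 (severe depression"). The planned output is stated in the same section: "A table with summary statistics for total scores and overall score interpretation categories will be presented". A listing is planned as well.

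Three other places bear on the point:

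- Protocol 8.3.8 says that "PHQ-9 will be self-administered during the screening visit". It gives no grade cut-offs.
- Protocol 5.2, exclusion criterion 15, removes people who "Display moderate to severe depression as indicated by the Participant Health Questionnaire" at screening.
- SAP 10 makes the safety analysis set the default for its analyses, and SAP 7.1 asks for counts and percentages for categorical variables. Neither says whether a percentage is taken over the whole set or only over participants who have a grade.

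**The concern.** The scoring rule and the grading rule in the same section do not match. The scoring rule allows a total of 0 (every item answered at its lowest level), but the grading rule starts at 1. If the table is programmed from this text, a participant with no symptoms gets no grade.

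The gap also lies where participants are likely to be. Exclusion criterion 15 removes moderate or worse depression, which on the SAP's own labels means totals of 10 or more. Participants analysed should therefore score 0 to 9. In that range only two of the five grades can be used, and the value without a grade is the lowest one.

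At stake is the accuracy of one descriptive table: whether its category rows account for everybody, and whether the shares shown for minimal and mild depression are right.

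**Working it through.** **Inputs.** Nine items scored 0 to 3, and the grades 1-4, 5-9, 10-14, 15-19 and 20-27 (SAP 10.10). About 100 participants planned (SAP 5.3). The share scoring 0 and the share scoring 5 to 9 are not in the documents, so both are assumptions below.

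**Step 1: the SAP's own maximum.** 9 × 3 = 27, which matches the stated figure. The same rule gives a minimum of 9 × 0 = 0. There are 28 possible integer totals, 0 to 27.

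**Step 2: coverage of the grades.** The grade widths are 4 + 5 + 5 + 5 + 8 = 27 totals. Checking each total from 0 to 27 against the five grades shows that 27 of the 28 fall in exactly one grade, none falls in two, and the only one not covered is 0.

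**Step 3: is a 0 dealt with elsewhere?** Protocol 8.3.8 has no cut-offs. The missing-data rules in SAP 7.2.4 cover the cataplexy diary, the NVAS and the ESS, but not the PHQ-9. In any case a 0 is an observed score, not a missing one. No separate row for 0 is defined.

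**Step 4: how many participants could be affected.** For an assumed share p of zero scores among 100 participants, the expected number without a grade is 100p, and the category rows over the full set add to 100(1 − p)%. The chance of at least one zero is 1 − (1 − p)^100.

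| Assumed share scoring 0 | Without a grade, of 100 | Category rows add to | Chance of at least one |
|---|---|---|---|
| 1% | 1 | 99% | 63% |
| 5% | 5 | 95% | 99% |
| 10% | 10 | 90% | over 99% |
| 20% | 20 | 80% | over 99% |
| 40% | 40 | 60% | over 99% |

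**Step 5: effect on the shares.** Assume that 20 of 100 score 5 to 9, that nobody scores 10 or more (exclusion criterion 15 applied on the SAP's grades), and that 20 or 40 score 0. Then 60 or 40 score 1 to 4.

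| Denominator | Mild (5-9) | Lowest grade as written (1-4) |
|---|---|---|
| Full set, 20 score 0 | 20/100 = 20% | 60/100 = 60% |
| Full set, 40 score 0 | 20/100 = 20% | 40/100 = 40% |
| Graded only, 20 score 0 | 20/80 = 25% | 60/80 = 75% |
| Graded only, 40 score 0 | 20/60 = 33% | 40/60 = 67% |

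With a first grade of 0-4 the figures would be 20% mild and 80% minimal in every row. The mild share is therefore wrong only under the graded-only denominator. Over the full set the mild share is right, and the fault shows as a shortfall in the lowest row and in the sum.

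**Step 6: after the correction.** With grades 0-4, 5-9, 10-14, 15-19 and 20-27, all 28 totals fall in exactly one category, with no gap and no overlap.

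**The case against.** The strongest case on the other side is that the gap does little harm.

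- The PHQ-9 is administered at screening only. It is neither a key nor an exploratory endpoint (SAP 4.2), and it is not among the baseline characteristics listed in SAP 8.3.
- A score of 0 cannot trigger exclusion criterion 15.
- Rows that fail to add to 100% are easily noticed when tables are checked, and most programmers would place a 0 in the lowest grade without asking.

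All of this stands as a limit on importance. It does not remove the fault, because a SAP should not rely on a programmer departing from its written ranges.

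Two stronger readings are tempting, and the documents support neither. A reader might infer that participants scoring 0 disappear from the PHQ-9 table altogether. They do not: the same table gives total-score statistics, to which they contribute, and they appear in the listing. Only the category rows miss them.

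A reader might also infer that the mild share will necessarily be overstated. That needs a denominator restricted to graded participants, and the SAP specifies none. Over the safety analysis set, which is the default for SAP 10, the mild share is correct. If zeros were displayed in a missing row within the full set, the mild share would again be correct, although observed scores would be mislabelled as missing.

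**Conclusion.** The point holds as an arithmetic inconsistency within SAP 10.10: its scoring rule allows 28 totals and its grades cover 27, leaving out 0. That part needs no assumption.

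The size depends on quantities the documents do not give. For assumed zero shares of 1% to 40%, about 1 to 40 of 100 participants would have no grade. Over the full set, the category rows would then add to between 99% and 60%, with the mild share unchanged. Only with a graded-only denominator, and assuming 20% mild with 20% to 40% scoring 0, would the mild share read 25% to 33% instead of 20%.

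The consequence is minor and stays within one descriptive table. No eligibility decision, effectiveness summary or adverse event result uses these grades.

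**What to change.** In SAP 10.10, change the first grade from 1-4 to 0-4. Alternatively, keep 1-4 and add a separate row for a total of 0. Either way, every total from 0 to 27 then falls in exactly one category. It would help to state in the same place that the percentages use the safety analysis set, with participants who have no PHQ-9 total shown in a row of their own.

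The cost is one number (or one added row) in the SAP and the matching change in the programming format. No data collection, eligibility rule or other analysis is affected.
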